12.4. Safety Monitoring

The intervention phase of this study will occur while the participant is in the ICU, where constant medical care and observation are provided, so initial responses to adverse events will be in charge of the care team because they are the best suited for an on-time reaction. If emergent adjustments to the treatment plan are needed, those will be decided by the care team in direct communication with the research team when the time allows it. This communication will ensure compliance with the intervention criteria whenever possible, even if it implies switching an ASM for another one listed on the intervention protocol. Every adverse event related to a study subject being reported to the SAFE reporting system or identified by other non-specified means will be tracked by the study coordinator, who will inform the research team and the ISM, who will first decide if there is an identifiable unanticipated problem involved with the AE and then review the event to define its grade, its likelihood of being related to the study, the potential risk of recurrence, and how to prevent it. The ISM is free to schedule a meeting to complete those tasks, with the assistance of whom he determines. After the adverse event analysis, a study AE report classifying the event will be created (appendix N), and the AE that are not classified as

unrelated will be included in the reported safety variables. In case of severe adverse events, the meeting will also state the necessary conditions to resume the study or its definite early termination.

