12.2. Assessment of Safety

The present study includes vulnerable populations unable to give consent which is addressed by LAR’s informed consenting process. It does not involve experimental drugs and employs clinical safety measures to prevent complications during the transport and scanning of the patients. Nonetheless the potential AE of diagnostic procedures and the ASM used for the intervention will be assessed by the following strategies:

- Eligibility criteria that imply checking for hypersensitivity or contraindications to the treatment protocol options that could be selected as the patient’s intervention. A selection of the non-contraindicated list of ASM for potential intervention use since the enrollment time reinforces this approach.
- Clinically indicated routine blood cells count, hepatic function, and renal function.
- Implementation of the clinical monitoring plan.
- Frequent direct communication between the care team and the research team.
- Severe adverse events (SAE) in enrolled subjects will pause the trial enrollment.
- The Independent Safety Monitor (ISM) will classify and report the AE. He will decide in which cases a meeting with the research or the care teams is needed for that task, and the assistants to the meeting. In case of mild to moderate adverse events found to be related, the research personnel will present a mitigating strategy. In the case of a SAE, the ISM will decide the conditions required to resume the trial or study end.
- Collection and analysis of safety variables to reassure and evaluate AE non-repetition strategies.

As criteria for individual research stopping, SAE will lead to retirement from the study as well as grade 2 to 3 AE without adequate measures to solve the event and prevent its study-related recurrence. Other events that

render the subject non-compliant with the enrollment criteria such brain death will retire the patient even if their occurrence was not triggered by the research activities.

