12.3. Unanticipated Problems, Adverse Events, Serious Adverse Events

Unanticipated Problems: An unanticipated problem is any incident, experience or outcome that meets all three Office for Human Research Protections (OHRP) criteria (1) unexpected (in severity, specificity, frequency, or nature), (2) related or possibly related to the research, and (3) indicates that subjects or others are at a greater risk of physical, psychological, economic, legal, or social harm, as defined in UNC Office of human Research Ethics SOP.

Adverse Event (AE) Definitions: Any untoward or unfavorable occurrence in a human subject, including any abnormal sign (for example, abnormal physical exam or laboratory finding), symptom, or disease, temporally associated with the transportation and scanning time for the rs-fMRI#1 or rs-fMRI #2, or with the administration of one of the ASM listed as possible treatment protocol during the intervention phase, whether or not considered related to the subject's participation in the research.

Serious Adverse Events (SAE) Definition: Adverse event or suspected adverse reaction which is considered "serious" if, in the view of either the research team or the Neurology department, it results in any of the following outcomes:

- Death
- A life-threatening adverse event
- Prolongation of existing hospitalization, a persistent or significant incapacity or substantial disruption of the ability to conduct normal life functions.
- Important medical events that may not result in death, be life-threatening, or require hospitalization may be considered serious when, based upon appropriate medical judgment, they may jeopardize the patient or subject and may require medical or surgical intervention to prevent one of the outcomes listed in this definition. Examples of such medical events include severe dermatological reactions or blood dyscrasias.

Grading the Severity of Adverse Events and Events of 'Special Interest': AE non classified as unrelated will be classified according to the Common Terminology Criteria for Adverse Events (CTCAE) scale v5.0 (appendix M) as follows:

Phenobarbital

Respiratory, thoracic and mediastinal disorders					
CTCAE Term	Grade 1	Grade 2	Grade 3	Grade 4	Grade 5

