Aspartate aminotransferase increased	>ULN - 3.0 x ULN if baseline was normal; 1.5 - 3.0 x baseline if baseline was abnormal	>3.0 - 5.0 x ULN if baseline was normal; >3.0 - 5.0 x baseline if baseline was abnormal	>5.0 - 20.0 x ULN if baseline was normal; >5.0 - 20.0 x baseline if baseline was abnormal	>20.0 x ULN if baseline was normal; >20.0 x baseline if baseline was abnormal	-

Definition: A finding based on laboratory test results that indicate an increase in the level of aspartate aminotransferase (AST or SGOT) in a blood specimen.

Blood and lymphatic system disorders					
CTCAE Term	Grade 1	Grade 2	Grade 3	Grade 4	Grade 5
Eosinophilia	>ULN and >Baseline		Steroids initiated		
Definition: A disorder characterized by laboratory test results that indicate an increased number of eosinophils in the blood.					
Leukocytosis			>100,000/mm ³	Clinical manifestations of leucostasis; urgent intervention indicated	Death
Definition: A disorder characterized by laboratory test results that indicate an increased number of white blood cells in the blood.					

Relatedness Definition: The research team, the clinical team and the independent safety monitor (ISM) will assess the likelihood of every SAE to be related to the research procedures and will classify the AE as:

- Unrelated
- Unlikely related
- Possibly related
- Probably related
- Definitely related

Non-SAE AE will be classified just by the ISM, and in both cases (SAE and non-SAE), to do so they will consider the following criteria:

- The AE has been previously reported for the suspected relatedness of ASM
- The temporal association between the ASM administration time and the AE is consistent with evidence-based literature.
- Other potential causes for the suspected AE were considered.

AE not classified as Unrelated will be considered to intervene with protective measures.

Expectedness Definition: The study personnel will evaluate if the related AE/SAE was expected. AEs different from transitory ventilatory decoupling are not expected during transport to MRI scans. The incident, experience, or outcome potentially related to one ASM listed is expected if reported in the FDA Online Label Repository in terms of nature, severity and frequency (see appendix B to F), and it is congruent with the subject's clinical condition.

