AE and SAE Assessment, Follow-up Procedures: Multimodal monitoring and the daily paraclinical test indicated by the patient's clinical care will provide the means to detect the eventual AE. The research team and the ISM will actively search the medical charts for reported AE or concerning findings and establish direct communication with the care team to verify those findings to be considered an AE. Clinical conduct, including treatments required because an AE will be provided as needed by the care team, according to clinical management institutional guidelines. Meanwhile, the research team will verify the subjects' criteria to continue in the trial. For patients still able to continue in the study that presents an AE related to a specific intervention ASM, the care team and the research team will look to replace the related ASM with another from the protocol if that is safe for the patient and could let to complete the intervention criteria to perform the follow up tests. The clinical follow up required will be indicated by the care team and specific aims related follow up will be decided by the research team.

Reporting and Documentation Procedures: After the ISM analysis of each AE, the research team will report the event to the Neurology Department and the IRB by an NIH Clinical Research Toolbox Adverse event Form v2.0 (Appendix N). If the AE was classified as severity grade 4 or 5, or meets the UNC criteria for Promptly reportable information, it will be reported within seven days from the event; otherwise, the report will be stored at the clinical Resting State fMRI service and provided to the Neurology Department and the IRB as applicable. All those reports will be input in the corresponding safety variables and will be collected by the research team at the reporting time.

The Research team and the independent safety monitor will also look for any unanticipated problem (UP), which the study monitor will report it to the IRB and the Neurology Department with an NIH UP form (Appendix O), within seven days of the observed problem.

Participant Notification of New Information: Any new safety information known by the Research team will be provided to the actively enrolled subject or his LAR within five days and this communication will be reported in the electronic medical charts.

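### Section 12.4 keeps AEs classified as Unrelated out of the reported safety variables, and 12.3 keeps them out of CTCAE grading, against 12.3's own relatedness-free AE definition and its all-reports entry rule.

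*Combined protocol and SAP*

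**What the plan says.** Section 12.3 defines an AE as an unfavourable occurrence temporally associated with transport and scanning, or with a listed ASM during the intervention phase, "whether or not considered related to the subject's participation in the research". Its reporting paragraph says of the AE reports: "All those reports will be input in the corresponding safety variables". No relatedness condition is attached.

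The grading paragraph of 12.3 applies CTCAE v5.0 only to AEs that have not been classified as unrelated.

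Section 12.4 has each event reviewed for its grade and its likelihood of being related, and a report written on each. It then sets the rule for entry: AEs outside the lowest relatedness category, that is, those not judged "unrelated will be included in the reported safety variables".

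On who decides, 12.3 says: "The research team, the clinical team and the independent safety monitor (ISM) will assess the likelihood of every SAE to be related". For the rest: "Non-SAE AE will be classified just by the ISM". Section 12.2 makes no such split: "The Independent Safety Monitor (ISM) will classify and report the AE". Relatedness has five categories, from Unrelated to Definitely related. One of the three points to be considered is: "The AE has been previously reported for the suspected relatedness of ASM".

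In the variables table of section 4.3, the AE variables are named for events related to the transport or to the intervention. They are scaled 1 to 5 and assigned to no aim.

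**The concern.** A safety dataset normally holds every event that meets the AE definition and carries causality as a column. Here causality decides whether an event enters the reported variables at all.

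That matters more than usual in this design. Section 4 describes an uncontrolled, open-label, single-centre study in ICU patients with acute brain injury. Section 6 allows additional ASM and prohibits no concomitant therapy. Any event will have several plausible causes, and no comparator arm exists against which a wrong causality call would show up. An all-cause count does not depend on those calls; a count restricted by relatedness does.

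Grading is also at stake. Seven-day reporting (12.3), discontinuation of the intervention (7.8) and study suspension (12.5) all refer to AE grade. If events ruled Unrelated are not graded, the documents do not say how those rules treat them.

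**Working it through.** No arithmetic applies. The plan states no expected AE rate, no share of events expected to be ruled Unrelated, and no safety sample-size figure. The check is a comparison of the text.

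1. **What counts as an AE.** Under 12.3, relatedness plays no part; the limits are the transport and scan periods and ASM administration during the intervention phase.

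2. **What enters the safety variables.** The reporting paragraph of 12.3 says all AE reports. Section 12.4 says those not classified as unrelated. The 12.4 sentence does not contain the word only, but it has no function unless the remaining events stay out. For an event ruled Unrelated the two rules give opposite answers.

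3. **What is graded.** The grading paragraph of 12.3 covers AEs not classified as unrelated. Section 12.4 has the grade defined in the review of each event. Again the two differ for events ruled Unrelated. The table in 4.3 records AEs on a 1 to 5 scale, apparently the CTCAE grade, so an ungraded event would have no value to enter even under the all-reports rule.

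4. **Variable names.** The 4.3 table names the variables for related events. That fits the restriction in 12.4 and not the definition in 12.3, so the restriction is not an isolated phrase.

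5. **Who decides.** For SAEs, 12.3 names the research team, the clinical team and the ISM, with no rule for disagreement. For non-serious AEs it names the ISM alone. Section 12.2 reads as the ISM for all AEs. Section 12.4 makes no exception for serious events, so an SAE ruled Unrelated also falls outside the reported variables.

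6. **Whether another analysis makes up for it.** The aim-specific plans in 8.3 cover Aims 1 to 6 and contain no AE tabulation. Section 12.2 mentions analysis of the safety variables, but those are the variables that 12.4 restricts. No all-cause table is planned.

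7. **Whether the omitted events survive elsewhere.** They do. Section 12.4 creates a report for each AE, 12.3 has the reports stored or submitted, 10.2 has AEs entered in REDCap without a relatedness condition, and 7.8 collects reported AEs for dropouts. All-cause counts could be rebuilt from these records, although grades might be missing.

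**The case against.** The strongest reply is that the restriction is narrow and the records are complete. Only one of five categories is left out; events judged Unlikely related stay in. Every AE still has a report, and REDCap entry under 10.2 is not restricted. This stands, and it rules out a reading that a reader might reach from 12.4 alone: that events ruled Unrelated are discarded for good. The documents support omission from the reported variables, not loss.

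A reader might also infer that one person's judgement filters the whole safety result. Section 12.3 does not support that: sole classification by the ISM applies to non-serious AEs, and three parties assess each SAE.

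A third inference is that a new or interaction effect of two combined ASMs would be ruled Unrelated because it has not been reported before. Prior reporting is only one of three considerations, beside timing and other causes, and no rule makes an unlabelled event Unrelated. Unexpected, possibly related events that indicate greater risk also have the unanticipated-problem route, with seven-day reporting, and 12.4 takes that decision first. The criterion leans towards familiar effects, but the stronger claim is not shown.

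Last, a reader might say that the later placebo-controlled trial would be planned on an understated AE rate. Section 4.2 ties that planning to SzNET response and its correlation with EEG, and 4.3 ties feasibility to enrollment and dropout. Section 2.2 does list medication side effects, morbidity and mortality among the outcomes whose collection the pilot will test, but no document says that the AE rate will be a design input.

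None of this reconciles the entry rules or the grading rules, and none supplies an all-cause table.

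**Conclusion.** The point holds as a contradiction with a consequence for reporting. If 12.4 and the grading paragraph of 12.3 are followed as written, the reported safety result omits events ruled Unrelated, serious or not, and understates the all-cause AE burden whenever there are such events. If the reporting paragraph of 12.3 is followed instead, it does not. The plan does not say which governs.

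The size of the understatement cannot be derived. It equals the share of AEs ruled Unrelated, for which the documents give no figure and no basis for a range. The conclusion rests on reading 12.4 as leaving those events out, which is the only reading that gives the sentence an effect, and on the absence of any AE analysis in section 8. This should be corrected before safety results are tabulated. It does not show that safety data will be lost.

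**What to change.** - Reconcile 12.3 and 12.4 so that every AE meeting the 12.3 definition is graded and entered in the safety variables, with the five-level relatedness classification stored as an attribute of the event.
- Rename the AE variables in the 4.3 table so that they are not confined to related events.
- Align 12.2 with 12.3 on who judges relatedness for SAEs and for non-serious AEs, and state how disagreement over an SAE is settled.
- Add to section 8 a descriptive safety table giving all-cause AE and SAE counts by grade first, then the subset not classified as Unrelated.

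The cost is a few sentences across these sections and one extra table. A report is already created for each AE; the added work is to grade and enter the events ruled Unrelated. No dose, stopping rule or other clinical rule needs to change, but the sections whose rules refer to AE grade (7.8, 12.3 and 12.5) should be read against the reconciled text.

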12.5. Study Suspension / Early Termination of the Study

The Study will be suspended and potentially prematurely terminated in the following situations:

- A severe adverse event occurs, and there is a concern for the risk of recurrence without an immediate and reliable preventive strategy.
- Happen three recurrent grade 2 to 3 AE of the same type implying noncompliance or inefficacy of the corrective measures.
- Notice of an *unanticipated problem* that implies an unfavorable risk benefit relationship for the intervention to the target population.
- The 25 percent of the maximum number of subjects to be enrolled have had the rs-fMRI#1 and no SzNET have been detected.
- A cumulative number of five enrolled patients allocated to the intervention do not reach to complete the intervention phase and get the research follow up tests.
- Any determination of serious or continuing noncompliance by the reviewing IRB.

If any of these situations is identified, it will prompt an asynchronous meeting or in person meeting, as determined by the ISM, for the research team to present an action plan to the Vice Chair of Research of the Department of Neurology. The Vice Chair will then assess the conditions for resuming the study, consider early termination if necessary, or convene a broader meeting as deemed appropriate. For those AE involving suspension and determination of being study-related, the resuming asynchronous or in person meeting will include the assistance of the ISM and whoever s/he determines as appropriate for the AE analysis.

13. Regulatory, Ethical, and Study Oversight Specifications

13.1. Informed Consent Process

The informed consent for the BIS screening test will be obtain verbally and the study's informed consent will be obtained using the informed consent form. Please see further details in section 13.1.2

13.1.1. Consent/Accent and Documents Provided to Participants

Consent forms describing in detail the study intervention, study procedures, and risks are given to the participant and written documentation of informed consent is required prior to starting intervention/administering study intervention. The following consent materials are submitted with this protocol:

- Appendix P. Informed consent form.
- Appendix B FDA insert of Fosphenyton
- Appendix C FDA insert of Lacosamide
- Appendix D FDA insert of Levetiracetam
- Appendix E FDA insert of Phenobarbital
- Appendix F FDA insert of Valproate

13.1.2. Consent Procedures and Documentation

Informed consent is a process that is initiated prior to the individual's or their LAR's agreeing to participate in the study and continues throughout the individual's study participation.

The first approach to the patient's LAR will be by telephone, presenting the researcher as non-care team personnel, part of a research team from the neurology department, and explaining the purpose of the call with a general idea of the study; then will ask for consent to schedule a personal interview to give further details of the study and the screening procedures. If the LAR accepts, an interview will be scheduled soon, in English or Spanish, according to the LAR preferences. The interview can be performed by one of the study investigators or by the research coordinator who will be trained to perform this activity.

At the interview, the screening process and the Barthel Index will be explained, if the LAR agree to continue the screening, the Barthel Index will be completed. For patients with a Barthel score of 75 or less the researcher will explain that the patient is not eligible for the study, in the case of a Barthel score of 80 or more the researcher will continue with the informed consent process to enroll the patient.

Consent forms will be Institutional Review Board (IRB)-approved and the participant's LAR will be asked to read and review the document. The investigator will explain the research study to the participant's LAR and answer any questions that may arise. A verbal explanation will be provided in terms suited to the LAR's comprehension of the purposes, procedures, and potential risks of the study and of their rights as research participants. Participant's LAR will have the opportunity to carefully review the written consent form and ask questions prior to signing. The participant's LAR should have the opportunity to discuss the study with their family and think about it prior to agreeing to authorize the participation. The participant's LAR will sign the informed consent document prior to any procedures being done specifically for the study. Participant LAR must be informed that participation is voluntary and that subjects may withdraw from the study at any time, without prejudice. A copy of the informed consent document will be given to the participant LAR for their records. The informed consent process will be conducted and documented in the source document (including the date), and the form signed, before the participant undergoes any study-specific procedures. The rights and welfare of the participants will be protected by emphasizing to their LAR that the quality of their medical care will not be adversely affected if they decline to participate in this study. In case a research subject regains capacity to consent by neurological and mental medical exam, the research team will explain to the subject their current situation in the study and will explain all the study dispositions mentioned before to request for new consent. If the participant doesn't want to continue in the study, no further research studies will be performed, or new information collected, but the information obtained until that moment will be included in the study analyses.

